Study Drug Accountability		X	X	X	X	X	X	
Study Drug Dispensation		X		X				
Observed Dosing		X	X	X				Participants must take their study drug in the clinic for observed dosing on Day 1, Week 4, and Week 12.

CBC = complete blood count; CD4+ = clusters of differentiation 4; DNA = deoxyribonucleic acid; DBS = dried blood spot; ESDD = early study drug discontinuation; GFR = glomerular filtration rate calculated using the Cockcroft-Gault equation; HBV = hepatitis B virus; HCV = hepatitis C virus; HIV-1 = human immunodeficiency virus type 1; HIVTSQs = HIV treatment satisfaction status questionnaire [quantitative]; HIVTSQc = HIV treatment satisfaction change questionnaire [quantitative]; RNA = Ribonucleic acid; PK = pharmacokinetic(s); TFV-DP = tenofovir diphosphate.

- a Evaluations to be completed within 42 days prior to Day 1 visit.
- b Participants will be dispensed study drug at the Day 1 visit; initiation of treatment with the study drug must take place in the clinic for observed dosing at Day 1 visit.
- c All study visits are to be scheduled relative to the Day 1 visit date. Visit windows are  $\pm 2$  days of the protocol-specified date through Week 12,  $\pm 6$  days of the protocol-specified date for Week 24. For the purpose of scheduling a 30-day follow-up visit, a  $\pm 6$ -day window may be used. Those participants who prematurely discontinue study drug and continue in the study through at least one subsequent visit after the early study drug discontinuation visit will not be required to complete the 30-day follow-up visit.
- d Only applies to participants who miss the Week 24 visit, and must be completed within 30 days of discontinuing study drug.
- e Early study drug discontinuation visit to occur within 72 hours of last dose of study drug.
- f Chemistry profile: alkaline phosphatase, AST, ALT, total bilirubin, direct and indirect bilirubin, total protein, albumin, bicarbonate, BUN, calcium, chloride, creatinine, glucose, potassium, and sodium.
- g For any post-Day -1 visit, if the HIV-1 RNA value is  $\geq 50$  copies/mL, a retest should be performed at a scheduled or unscheduled visit 2-4 weeks after the date of the original test.

- h Hepatitis B virus surface Antigen (HBsAg), Hepatitis B core antibody (HBcAb), and Hepatitis C virus (HCV) serologies (reflex HCV RNA is performed in participants with positive HCV Ab serology)

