- i Metabolic Assessments: Fasting lipid panel (total cholesterol, HDL, direct LDL, triglycerides). If the participant has not fasted prior to the visit, the visit may proceed, but the participant must return within 72 hours in a fasted state.\
- j A single PK plasma sample will be collected at Day 1 prior to dose. A single trough plasma PK sample approximately 23 to 24 hours after the previous B/F/TAF dose and prior to B/F/TAF dosing on Weeks 4, 12, and 24, and a single postdose plasma PK sample at approximately 2 hours post B/F/TAF dose, witnessed by the study staff, at Weeks 4, 12, and 24 will be collected
- k HIV-1 genotype/phenotype resistance testing (which includes protease, reverse transcriptase, and integrase testing) only conducted for participants with confirmed virologic failure with HIV-1 RNA value  $\geq$  50 copies/mL. Participants should be managed according to [Figure 2](#). Following virologic rebound, participants will be asked to return to the clinic (2-4 weeks later) prior to the next scheduled visit or at the next scheduled study visit, for an HIV-1 RNA and HIV-1 genotype and phenotype blood draw. Based on the results of this testing, participants should be managed according to the Virologic Rebound Schema ([Figure 2](#)). Participants with HIV-1 RNA  $\geq$  50 copies/mL at Week 12 and/or 24 will be asked to return for an unscheduled visit within the visit window for a retest. Participants with HIV-1 RNA  $\geq$  200 copies/mL at ESDD, last visit, or Week 12 or 24 will also have resistance testing conducted.

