3.5. Missing Data and Outliers

3.5.1. Missing Data

Missing data can have an impact upon the interpretation of the trial data. In general, missing data will not be imputed unless methods for handling missing data are specified as follows.

- A missing pre-treatment laboratory result would be treated as normal (ie, no toxicity grade) for the laboratory abnormality summary.
- For missing last dosing date of study drug, imputation rules are described in Section 4.2. The handling of missing or incomplete dates for AE start is described in Section 7.2.6.2, and for prior and concomitant medications in Section 7.5.
- Missing PK sampling dates may be imputed based on other visit information. Missing PK sampling times may be imputed to nominal times. Missing drug concentrations will not be imputed.
- All available data for participants who do not complete the study will be included in the data listings.

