3.7.2. Analysis Visit Windows

Participant visits might not occur on protocol-specified days. Therefore, for the purpose of analysis, observations will be assigned to analysis windows for all analysis except PK analysis.

The analysis windows for Plasma HIV-1 RNA, Hematology, Chemistry, Urinalysis and Urine Pregnancy Laboratory Tests, Vital Signs and Weight are provided in Table 3-1.

The analysis windows for CD4+ cell count, CD4 %, estimated GFR_{CG} (Estimated GFR according to the Cockcroft-Gault formula for creatinine Clearance), and Metabolic Assessments (including fasting glucose and lipid panel: total cholesterol, high density lipoprotein [HDL], direct low density lipoprotein [LDL], triglycerides, and total cholesterol to HDL ratio) are provided in Table 3-2.

Analysis windows for the HIVTSQs are provided in Table 3-3.

HIVTSQc and Qualitative Interviews (English only) are to be completed by the participant at Week 4 with analysis window shown in Table 3-4.

A study-specific questionnaire will be completed by the participant on Day 1 (Baseline) and Week 4 with analysis window shown in Table 3-5.

Table 3-1. Analysis Visit Windows for Plasma HIV-1 RNA, Hematology, Chemistry, Urinalysis and Urine Pregnancy Laboratory Tests, Vital Signs and Weight

Visit	Study Day	Visit Window Study Day	
		Lower Limit	Upper Limit
Baseline	1	(none)	1
Week 4	28	2	56
Week 12	84	57	126
Week 24	168	127	210

Table 3-2. Analysis Visit Windows for CD4+ Cell Count, CD4 %, eGFR_{CG}, and Metabolic Assessments

Visit	Study Day	Visit Window Study Day	
		Lower Limit	Upper Limit
Baseline	1	(none)	1
Week 12	84	2	126
Week 24	168	127	210

Table 3-3. Analysis Visit Windows for HIVTSQs

Visit	Study Day	Visit Window Study Day	
		Lower Limit	Upper Limit
Baseline	1	(none)	1
Week 12	84	2	126
Week 24	168	127	210

Table 3-4. Analysis Visit Windows for HIVTSQc and Qualitative Interview

Visit	Study Day	Visit Window Study Day	
		Lower Limit	Upper Limit
Week 4	28	2	56

Table 3-5. Analysis Visit Windows for Additional Study Specific Questions

Visit	Study Day	Visit Window Study Day	
		Lower Limit	Upper Limit
Baseline		(none)	1
Week 4	28	2	56

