7.3.2.1. Treatment-Emergent Laboratory Abnormalities

Treatment-emergent laboratory abnormalities are defined as values that increase at least 1 toxicity grade from baseline at any time after baseline and up to and including the date of last dose of study drug plus 30 days, will be summarized. The incidence of treatment-emergent laboratory abnormalities and Grade 3 and 4 laboratory abnormalities will also be summarized. If baseline data are missing, any graded abnormality (ie, at least a Grade 1) will be considered treatment emergent). The maximum postbaseline toxicity grade will be summarized by laboratory parameter.

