7.3.3. Metabolic Laboratory Evaluations

For metabolic assessments, including fasting glucose and the lipid panel (ie, total cholesterol, triglycerides, LDL, HDL, total cholesterol to HDL ratio), only those measurements under fasting status will be summarized.

Median (Q1, Q3) of change from baseline in fasting metabolic assessments over time will be plotted by treatment group.

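### For a participant unfasted on Day 1, the fasted make-up lipid sample falls after the first dose, so a pre-existing Grade 3-4 lipid value can count as treatment-emergent in the laboratory co-primary endpoint

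*Protocol*

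**What the plan says.** **Schedule.** Protocol Section 11.3, Table 3, marks the metabolic assessments at Day 1, Week 12 and Week 24. Screening, the early-discontinuation (ESDD) visit and the 30-day follow-up have no mark. The screening chemistry profile does not fill the gap, because footnote f lists no lipids: "Chemistry profile: alkaline phosphatase, AST, ALT, total bilirubin, direct and indirect bilirubin, total protein, albumin, bicarbonate, BUN, calcium, chloride, creatinine, glucose, potassium, and sodium".

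**Unfasted visits.** Footnote i provides that, for a participant who has not fasted, "the visit may proceed, but the participant must return within 72 hours in a fasted state". It makes no exception for Day 1. Footnote b adds that "initiation of treatment with the study drug must take place in the clinic for observed dosing at Day 1 visit".

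**Baseline.** SAP 3.7.4 and 7.3.1 take the last value no later than first dose; 7.3.1 goes by date and time. The SAP table headed "Table 3-2. Analysis Visit Windows for CD4+ Cell Count, CD4 %, eGFR_{CG}, and Metabolic Assessments" closes the baseline window on Study Day 1 and gives Study Days 2 to 126 to Week 12.

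**Missing baseline.** SAP 3.5.1: "A missing pre-treatment laboratory result would be treated as normal (ie, no toxicity grade) for the laboratory abnormality summary". SAP 7.3.2.1: "If baseline data are missing, any graded abnormality (ie, at least a Grade 1) will be considered treatment emergent". Protocol 8.3.2 and 8.6.3 carry the same two rules.

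**Endpoint.** SAP 7.1 makes treatment-emergent Grade 3 or 4 laboratory abnormalities through Week 12 a co-primary endpoint. Lipids are among the safety laboratory measurements (Protocol Table 1, SAP Appendix 2), and no lipid exclusion is stated. For metabolic summaries, SAP 7.3.3 says that "only those measurements under fasting status will be summarized".

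**The concern.** Day 1 is the only planned pre-dose lipid measurement, and it is the one visit at which the order of sample and dose matters. The 72-hour allowance is harmless at Weeks 12 and 24. At Day 1 it can turn the intended baseline into a post-baseline value.

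Three things are at stake. A lipid abnormality that was present before the switch and has not changed can be counted in a co-primary endpoint. Change from baseline in lipids is lost for that participant, although Protocol Section 1.5 names lipid changes among the risks of antiretroviral drugs. And if no later lipid sample is taken by Day 126, a sample from the first days of treatment is reported as Week 12. The error in the co-primary always goes towards more events.

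**Working it through.** The plan has no figure of its own to reproduce: SAP 1.3 says that no sample size calculation was made. The check traces the rules and then sizes one misclassified participant.

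**1. Where the make-up sample falls.** SAP 3.7.1 gives Study Day = assessment date − first dosing date + 1. First dose is at the Day 1 visit, and a return within 72 hours is 0 to 3 calendar days later.

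| Days after Day 1 visit | Study Day | SAP Table 3-2 window |
|---|---|---|
| 0 | 1 | Baseline by date, but after the dose, so not baseline under SAP 7.3.1 |
| 1 | 2 | Week 12 |
| 2 | 3 | Week 12 |
| 3 | 4 | Week 12 |

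**2. How it is graded.** Take a participant with Grade 3 on a lipid test before the switch, unchanged afterwards, and no pre-dose lipid value.

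- As written: baseline missing, so Grade 0. The make-up value is Grade 3, a rise of 3 grades, and is treatment-emergent. The Week 12 value is also Grade 3 and also treatment-emergent. The participant counts.
- With a pre-dose fasted value: baseline Grade 3, later values Grade 3, rise of 0. The participant does not count.

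The definition in SAP 7.3.2.1 covers any time after baseline. Choosing one record per window does not remove the event.

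**3. What happens in by-visit summaries.** SAP 3.7.4 selects the record nearest the nominal day, which is Day 84 for Week 12. A make-up sample on Day 2 to 4 is 84 − 4 = 80 to 84 − 2 = 82 days away, so a genuine Week 12 sample displaces it. Without one, the make-up sample is the only record in the Day 2 to 126 window.

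**4. Size of one misclassified participant.** Inputs: n = 35 (Protocol 4.1), assuming all have post-baseline values; two-sided exact 95% interval (Protocol synopsis). Each participant moves the estimate by 1/35 = 2.9 percentage points.

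| Events / 35 | Estimate | Exact 95% CI |
|---|---|---|
| 0 | 0% | 0 to 10.0% |
| 1 | 2.9% | 0.1 to 14.9% |
| 2 | 5.7% | 0.7 to 19.2% |

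**5. How many to expect.** The documents give neither the share unfasted on Day 1 (u) nor the share with pre-existing Grade 3-4 fasting lipids (g). Both are assumptions here, taken as independent, and no usable pre-dose value is assumed to exist. Expected number = 35 × u × g; chance of at least one = 1 − (1 − u × g)^35.

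| u | g | Expected | Chance of at least one |
|---|---|---|---|
| 5% | 2% | 35 × 0.001 = 0.04 | 3.4% |
| 10% | 5% | 35 × 0.005 = 0.18 | 16.1% |
| 30% | 10% | 35 × 0.03 = 1.05 | 65.6% |

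**The case against.** The strongest objection is that one link is not written down. The fasting-only sentence in SAP 7.3.3 governs metabolic summaries, and the grading sections (SAP 7.3.2 to 7.3.2.2) do not repeat it. Footnote i does not say that no lipid sample is drawn on an unfasted Day 1. If one is drawn before dosing, it meets the baseline definition in SAP 7.3.1, the baseline grade is not missing, and the false count need not occur. This stands: the point is conditional on there being no pre-dose lipid value. What remains is that the plan does not say which sample supplies the graded lipid baseline.

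Further points that stand:

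- Scoring a missing baseline as normal is prespecified and errs towards counting harm. The study is descriptive, without formal testing (SAP 3.4), so no stated decision turns on one event.
- The by-participant listing in SAP 7.3.2.2 shows all results for an affected test, so an attentive reader could see the missing pre-dose value. The reported proportion would still include the event.
- A participant already counted for another Grade 3-4 test adds nothing.
- A same-day return is possible. It then falls between two SAP rules, one by date and one by date and time.

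A reader might also infer more than the documents support. The event would not enter the co-primary as caused by B/F/TAF, because the laboratory endpoint has no relatedness component; only the adverse-event co-primary does. Change from baseline is not lost for every metabolic test, because glucose is in the screening chemistry profile and a fasted screening value could serve as baseline. The make-up sample does not generally replace the Week 12 value.

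**Conclusion.** The concern holds in conditional form. Where a participant is unfasted on Day 1 and has no pre-dose lipid value, the written rules count an unchanged pre-existing Grade 3-4 lipid value as treatment-emergent in a co-primary endpoint and remove that participant's lipid change from baseline. The rules conflict with the evident purpose of a Day 1 panel, and nothing in either document lets the make-up sample serve as baseline.

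The likely number affected is 0 or 1 of about 35, at 2.9 points each. That count rests wholly on assumed rates. The 65.6% chance of at least one event needs both assumptions at their upper end and should not be quoted as a forecast. The grading scale is only linked (Protocol Section 11.6), so the lipid cut-offs could not be checked.

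Severity is minor to moderate. It is worth settling because the estimate is a small proportion, the study is open-label, and the choice of baseline sample should be fixed before results are reviewed.

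**What to change.** **SAP.** In 3.7.4, 7.3.2.1 and Table 3-2, state that for fasting lipids with no fasted pre-dose value, the Day 1 make-up sample (taken within 72 hours of the Day 1 visit) is the reference for grading and for change. State also that it cannot be used as a post-baseline or Week 12 value. This settles the role of any unfasted Day 1 sample and the same-day return.

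**Sensitivity report.** Flag the affected participants. Report the laboratory co-primary with and without the lipid parameters that lack a pre-dose fasting value. This is needed because the rule uses a post-dose sample as reference.

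**Protocol.** If enrolment is still open, amend footnote i so that the fasted Day 1 lipid panel may be drawn at any time between screening and first dose. The SAP describes study visits in the past tense, so this may come too late. The SAP change need not, since SAP Section 1 says that the SAP is finalized before the database is.

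**Effect and cost.** An unchanged Grade 3-4 value is no longer counted, which lowers the estimate by 1/35 = 2.9 points per affected participant; one such event would go from 1/35 to 0/35. The SAP change costs a few sentences and one extra line of output, with no new samples. The downside is up to 3 days of drug exposure in the reference value of the few affected participants, which could mask a very early rise. The version without those lipid parameters shows how much the result depends on that choice.

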## 11.4. Questionnaires, Participant Provided Outcomes

### 11.4.1. Item content of the HIVTSQs and HIVTSQc

		HIVTSQs	HIVTSQc
Item no.	Item label [Suffix (c) denotes item label in the change version]	Item wording	Response options 6–0
Instructions			Instructions
1	Current treatment	How satisfied are you with your current treatment?	Very satisfied 6 to 0 very dissatisfied
2	Control	How well controlled do you feel your HIV has been recently?	Very well controlled 6 to 0 very poorly controlled
3	Side effects	How satisfied are you with any side effects of your present treatment?	Very satisfied 6 to 0 very dissatisfied
4	Demands	How satisfied are you with the demands made by your current treatment?	Very satisfied 6 to 0 very dissatisfied
5	Convenience	How convenient have you been finding your treatment to be recently?	Very convenient 6 to 0 very inconvenient
6	Flexibility	How flexible have you been finding your treatment to be recently?	Very flexible 6 to 0 very inflexible
7	Understanding	How satisfied are you with your understanding of your HIV?	Very satisfied 6 to 0 very dissatisfied
8	Lifestyle	How satisfied are you with the extent to which the treatment fits in with your lifestyle?	Very satisfied 6 to 0 very dissatisfied
9	Recommend to others	Would you recommend your present treatment to someone else with HIV?	Yes I would definitely recommend the treatment 6 to 0 No I would definitely not recommend the treatment
10	Continue	How satisfied would you be to continue with your present form of treatment?	Very satisfied 6 to 0 very dissatisfied
11	Easy/difficult	How easy or difficult have you been finding your treatment to be recently?	Very easy 6 to 0 very difficult
12	Pain/discomfort	How satisfied are you with the amount of discomfort or pain involved with your present form of treatment?	Very satisfied 6 to 0 very dissatisfied

Please make sure that you have circled one number on each of the scales.

**11.4.2. Study GS-US-380-6738 Qualitative Participant Interview Guide**

Guide begins on the following page.

# **Study of GS-US-380-6738: B/F/TAF in Participants Switching from CAB + RPV to B/F/TAF for HIV-1 infection.**

## **B/F/TAF Participant Interview Guide**

| JULY 24, 2023 | Version 1.0

Participant ID:  
Interviewer Initials:  
Interview Date:

Participant Interview Guide CAB+RPV switch study

Participant ID Number: \_\_\_\_\_ Date of Interview: (month/day/year) \_\_\_\_\_ Interviewer Initials: \_\_\_\_\_

**PROJECT BACKGROUND AND INSTRUCTIONS *(for Interviewer only)***

The objective of this qualitative component of study GS-US-380-6738 is to understand experience with injectable and oral therapy for HIV-1 treatment for people with HIV (PWH) by exploring experiences on CAB+RPV, also known as Cabenuva, reasons for switching from CAB+RPV to B/F/TAF, also known as Biktarvy, experiences post switch on daily oral B/F/TAF, and preferences for injectable and oral therapy.

This discussion guide is designed to help focus the conversation but should not be used as a verbatim script. Probes and questions may change slightly depending on participant feedback. Additional unscripted probes to be used to gain further information or clarification may include:

- Clarification (e.g., I don't quite understand that)
- Expressing understanding (e.g., How did you cope with that?)
- Justification (e.g., What makes you say that?)
- Importance (e.g., I'm not sure I understand how these two things are linked; please could you explain this to me?)
- Extending narrative (e.g., Please tell me a bit more about that)
- Accuracy (e.g., Let me see if I understand that)

Introductory statements are in regular text; the main questions are **bolded**, and follow-up probes are in italics. Please note that **instructions to the interviewer are in red font** throughout this guide and should not be read to the participant.

Do not repeat questions for information that the participant has already provided unless more information is needed. Manage the conversation to complete the interview within the allotted 60 minutes.

Proprietary and Confidential | Page 2

Participant Interview Guide CAB+RPV switch study

Participant ID Number: \_\_\_\_\_ Date of Interview: (month/day/year) \_\_\_\_\_ Interviewer Initials: \_\_\_\_\_

**INTRODUCTION (for Study Participant, 2-3 minutes)**

Good (*morning /afternoon/ evening*). I am <*interviewer name*>, a <*title*> with Cerner Enviza, a healthcare research group that is helping to coordinate this interview on behalf of Gilead. We are interviewing you today to understand your experience being treated with injectable CAB + RPV (Cabenuva) and oral B/F/TAF (Biktarvy). We will discuss how you learned about Cabenuva and Biktarvy, your experiences receiving the two treatments, and your thoughts on why you switched from Cabenuva to Biktarvy.

We agreed to talk for about an hour – does this time still work for you?

Before we start, I want to thank you for your participation.

What you tell me today is treated as private and confidential. Your answers will be combined into an aggregated report, and while we may use individual quotes to support findings from this research study, we will never use your real name or include any other personal information that could identify you.

We will be discussing topics that may be sensitive, and you may ask to skip any question(s). You also have the right to end this interview at any time and for any reason. There are no right or wrong answers, please answer each question to the best of your ability.

We are required to pass on to Gilead, who is a maker of medicines, details about any kind of side effects or complaints that are related to their products that are mentioned during the interview. If this happens, we will need to collect details and report the event, even if you have already reported it directly to the company or the regulatory authorities. You will be asked whether you consent to us passing your details to the client company's drug safety department for their follow up, but you may choose to remain anonymous. This will have no impact on the confidentiality and anonymity associated with the interview itself.

Are you comfortable proceeding with the interview on this basis?

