### **6.5.1.4. Qualitative Interviews (English only)**

Among the participants who are recruited and consented to undergo qualitative interviews, a vendor will schedule face to face (or telephone) interviews with these participants in English over a video communication platform. Interviews will cover topics such as reasons for switching to B/F/TAF; experiences using CAB+RPV, including injection site reactions, side effects, time spent via clinic visits, etc; preferences for injectable and oral HIV medications; and treatment satisfaction post switch. Interviews will be recorded and transcribed for data analysis purposes. The qualitative interview will occur near the Week 4 visit (visit window range Week 3-9). Refer to [Appendix 11.4.2](#) for qualitative interview guide.

The qualitative interviewer would be responsible for notifying the investigator of all the AE's/SAE's/SSR's identified during the interview within 24 hours of awareness. Please refer to [Section 7.4](#) for the reporting process.

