## **7.2. Assessment of Adverse Events and Serious Adverse Events**

The investigator or qualified subinvestigator is responsible for assessing AEs and SAEs for causality and severity, and for final review and confirmation of accuracy of event information and assessments.

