#### **7.3.2.       Adverse Events**

Following initiation of study drug, collect all AEs, regardless of cause or relationship, until 30 days after administration of the last dose of study drug and report the AEs on the eCRFs as instructed.

All AEs and clinically significant laboratory abnormalities should be followed until resolution or until the AE is stable, if possible. Gilead may request that certain AEs be followed beyond the protocol-defined follow-up period.

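### The interview guide's introduction conflicts with Protocol 6.5.1.4 on who is told about adverse events, which events are covered, and whether they carry the study ID

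*Protocol*

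**What the plan says.** Protocol 6.5.1.4 sets the interviewer's duty: "The qualitative interviewer would be responsible for notifying the investigator of all the AE's/SAE's/SSR's identified during the interview within 24 hours of awareness". It then refers to Section 7.4 for the reporting process. It sets no condition on cause and gives the participant no choice about identification.

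The guide in Protocol 11.4.2 opens with a statement to the participant. It says the vendor has to pass to the sponsor "details about any kind of side effects or complaints that are related to their products that are mentioned during the interview". It adds that, if this happens, "we will need to collect details and report the event, even if you have already reported it directly to the company". It then says the participant will be asked to agree to "passing your details to the client company's drug safety department for their follow up, but you may choose to remain anonymous". The participant is asked whether they are comfortable going ahead on this basis, and the interview ends if they are not. The investigator and the 24-hour duty do not appear in the guide.

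On AEs generally, Protocol 7.3.2 has sites "collect all AEs, regardless of cause or relationship, until 30 days after administration of the last dose of study drug". Under Protocol 7.2 the investigator or a qualified subinvestigator "is responsible for assessing AEs and SAEs for causality and severity". SAP 7.2.3 uses the investigator's relatedness call in the analysis.

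**The concern.** The interview asks participants about their experience with both treatments, so it is a likely place for an event to come up that has not yet reached the site. The AE co-primary endpoint depends on the investigator hearing of the event, grading it and judging whether B/F/TAF may have caused it. The statement on which the participant agrees to go ahead describes a different route: to the sponsor, for product-related complaints, with a choice about being identified.

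An interviewer who keeps to that statement may not meet 6.5.1.4. One who meets 6.5.1.4 does something the participant was not told about. What is at stake is late or incomplete AE recording, and the direction of error is toward under-counting. Protocol 1.3 gives the undocumented overlap of BIC with residual CAB as a reason for the study. An event that a participant blames on lingering injections is therefore one the investigator should be able to assess.

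**Working it through.** **1. The two texts side by side**

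- Recipient. 6.5.1.4: the investigator. Guide: the sponsor.
- Scope. 6.5.1.4: all AEs, SAEs and special situation reports (SSRs). Guide: side effects or complaints tied to the sponsor's products. It is silent on everything else.
- Identification. 6.5.1.4: no option. Guide: the participant may withhold their details from the sponsor's drug safety department.
- Timing. 6.5.1.4: 24 hours. Guide: none given.

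**2. Which events fall into the gap**

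- An event the participant links to B/F/TAF is inside the guide's scope, because B/F/TAF is the sponsor's product.
- An event the participant links to the CAB+RPV injections, or to no cause, is outside the guide's wording but inside 6.5.1.4. The investigator could still judge it related to B/F/TAF (Protocol 7.2.1), and it would then count toward the endpoint if Grade 3 or 4.
- Missed doses: guide Question 24 asks about them. Protocol 7.1.4 classes a missed dose as a medication error and hence an SSR. A missed dose is not naturally a side effect or a complaint, so the guide's statement does not clearly cover something the interview itself elicits.

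**3. What else would catch the event**

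- Sites assess AEs at every visit (Protocol Table 3), including Weeks 4 and 12. There is no scheduled visit between those two, while interviews run from Week 3 to Week 9. An event raised at Week 5 could wait 12 − 5 = 7 weeks for the next scheduled assessment.
- SAP 7.2.5 reconciles SAEs between the clinical and safety databases. No matching check is described for non-serious AEs, although Protocol 3.5 lists interview transcripts as source data.

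For an event to be missing at the Week 12 count, two things must go wrong: the interviewer does not notify the investigator, and the event is not picked up at the site visits.

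**4. Size if one event were lost**

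Inputs: about 35 participants in total and about 10 in France who are not interviewed (Protocol 4.1), so at most about 35 − 10 = 25 interviews, or 25/35 = 71%. The plan uses two-sided 95% exact limits (Protocol 8.6.2). It states no sample-size calculation (Protocol 8.9), so there is no planned precision to reproduce.

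For zero events the upper limit is 1 − 0.025^(1/n). For one event it is the 97.5% quantile of a Beta(2, n − 1) distribution.

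- n = 35: 0/35 gives 1 − 0.025^(1/35) = 10.0%. 1/35 = 2.9%, with limits 0.07% to 14.9%.
- n = 25 (North America only, as in the Week 12 interim): 0/25 gives 1 − 0.025^(1/25) = 13.7%. 1/25 = 4.0%, with limits 0.1% to 20.4%.

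These figures show what losing one event would do. They say nothing about how likely a loss is, and the documents give no input for that probability.

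**The case against.** The strongest reply is that a disclosure to participants does not cancel an instruction to the interviewer. Section 6.5.1.4 still applies, and the guide says it is not to be read word for word. The first half stands: a trained interviewer can meet 6.5.1.4 whatever the introduction says. The second half helps little. The latitude given is for probes and questions, whereas the introduction is the basis on which the participant agrees to go ahead.

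Several stronger readings are tempting, and the documents do not support them.

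- A reader might infer that only product-related events leave the interview. The guide does not say so. It is silent on other events.
- A reader might infer that anonymity lets a participant block the report or makes it untraceable. The guide says the event is reported in any case, and the choice concerns the participant's details for drug safety follow-up. The participant ID is on the guide's pages and is stated on the recording, so the vendor can link the event.
- A reader might infer that both co-primary endpoints are exposed. The laboratory endpoint comes from central laboratory results and cannot change by this route.
- A reader might infer a breach of the 24-hour SAE rule in 7.4.1.1. That clock starts when the investigator knows of the event. The weakness is that it may start late.
- A reader might take Weeks 3 to 9 as the period at risk. That is when interviews take place. Events from any time before the interview can be mentioned.

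Also fair: sites collect all AEs regardless of cause, and a Grade 3 or 4 event is unlikely to go unnoticed at both the Week 4 and Week 12 visits.

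**Conclusion.** The conflict between the guide's introduction and 6.5.1.4 is real and should be reconciled. It covers recipient, scope and identification. The consequence is modest: a small, indirect risk that AEs are recorded late or not at all, confined to the Grade 3 or 4 drug-related AE co-primary endpoint and the general AE and SSR records. A lost event also requires the site to miss it. The drop from 1/35 (upper limit 14.9%) to 0/35 (10.0%) is illustrative and is not an expected bias.

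This rests on three assumptions: about 25 North American participants at most are interviewed; interviewers may take their cue on reporting from the guide; and no separate vendor instruction, which would lie outside these documents, already resolves the difference. The consent pages were not available, so nothing is concluded about whether they agree with either text.

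**What to change.** **Guide wording.** Reword the introduction to match 6.5.1.4: any AE, SAE or SSR mentioned, whatever its cause, goes to the study investigator within 24 hours under the study ID. Missed doses should be clearly covered. The anonymity option need not be removed. Limit it to direct contact by the sponsor's drug safety department and to transcripts and quotations.

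**Interviews already held.** SAP 2.1 describes the Week 12 interim in the past tense. It was planned for after all North American participants had passed Week 12 or stopped study drug. If it has taken place, the interviews are probably complete and new wording will help only later use of the guide. The useful step is then to check the vendor's event log or the transcripts against the AE eCRF before database finalization, and to send unmatched events to the investigator for grading and causality. Any event added this way should be traced to the interim tables as well.

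**Cost.** One paragraph of guide text and a check of at most about 25 interviews. The small downside is that some participants may speak less freely once told that everything relevant goes to the study doctor.
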